6.8 Early Termination Visit

Subjects who discontinue taking study drug early should, if possible, have an Early Termination visit as soon as possible after the subject stops taking study drug. Where possible the Early Termination visit assessments should be completed in the study center as listed below. Site staff will need to provide subjects with meals and snacks at appropriate times during the visit to ensure subjects have enough energy prior to completing the exercise tests.

- Review concomitant medications and non-drug treatments*
- Review of adverse events*

- Brief physical examination (including weight)
- Physician completion of subjects PMM phenotypic description
- 12-lead ECG
- Vital signs (including temperature) *
- Obtain blood samples for:
 - Hematology (incl HbA1c)*
 - Biochemistry*
 - Additional bone and calcium metabolism markers
 - Plasma sample for pharmacokinetic analysis of REN001 *
- Obtain second morning void urine sample for:
 - Bone marker – NTX*
 - Urinalysis*
 - Drugs of abuse*
 - Urine for pregnancy testing (WOCBP only) *
- MFIS*
- BPI*
- SF-36*
- PGIS – muscle symptoms*
- PGIS – fatigue symptoms*
- PROMIS Short Form – FACIT Fatigue 13a*
- PGIC muscle symptoms (with respect to how they were on their last dosing day) *
- PGIC fatigue symptoms (with respect to how they were on their last dosing day) *
- WPAI:SHP*
- 12MWT
- 30STS
- Capsule counts of remaining capsules including any opened IMP bottles*
- Eye examination (may be completed \pm 14 days of the visit if required)

If the subject is unable to attend the Study Center for the full visit, then every effort should be made to complete the assessments marked with an asterisk (*) at the discretion of the Investigator this may be completed over 2 days if feasible.

If the subject is withdrawing from the study: after their Early Termination Visit they should be instructed to return for the Follow Up Visit 21-28 days after their last dose of study medication. If the Early Termination Visit is 21 or more days after the last dose, then the Follow Up Visit is not needed.

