6.9 Subject Continuation In Study Off IMP

If a subject discontinues taking study drug, they will be strongly encouraged to continue in the study for their Week 12 and Week 24 visits (see [Figure 3](#)). If they agree to remain in the study off-IMP as a minimum they will be requested to complete the following assessments:

- Review concomitant medications and non-drug treatments
- Review of adverse events

- Vital signs (including temperature)
- MFIS
- 12MWT

Table 2: Schedule of Activities

Time and Events Table	Screening	Baseline ^{1, 2} (Day 1)	Week 2 ³ (Day 14)	Week 4 ³ (Day 28)	Week 8 (Day 56)	Week 12 ^{2, 4} (Day 84)	Week 16 (Day 112)	Week 18 ³ (Day 126)	Week 20 (Day 140)	Week 24 ^{2, 4} (Day 168).	Early Term ^{2, 5}	Follow Up ³ (21-28 days post last dose)
Visit number	1	2	3	4		5		6		7		8
Window (days)			±3	±3		±7		±7		±7		
Informed Consent	X											
Completion of Proforma and data entered into eCRF ⁶	X											
Demographics	X											
Medical/medication/drug/alcohol/tobacco history ⁷	X											
Physician completion of PMM phenotypic description		X								X	X	
Physical exam ⁸	X	X				X				X	X	
12-lead ECG	X	X				X				X	X	
Supine Vital signs (BP, PR and temperature)	X	X	X	X		X		X		X	X	X
Serum FSH ⁹	X											
HbA1c	X									X	X	
Hepatitis B/C/HIV	X											
Safety labs (inc. urinalysis)	X	X ¹⁰	X	X		X		X		X ¹¹	X	X ¹¹
Blood sample for bone and calcium markers		X				X				X	X	
Pregnancy Test (WOCBP only) ¹²	X	X		X	X	X	X		X	X	X	X
Blood sample for genotyping ¹³	X											
Population PK blood sample ¹⁴		X	X	X		X		X		X	X	
Urine drugs of abuse	X	X				X				X	X	
Urine NTX		X				X				X	X	

Time and Events Table	Screening	Baseline ^{1, 2} (Day 1)	Week 2 ³ (Day 14)	Week 4 ³ (Day 28)	Week 8 (Day 56)	Week 12 ^{2, 4} (Day 84)	Week 16 (Day 112)	Week 18 ³ (Day 126)	Week 20 (Day 140)	Week 24 ^{2, 4} (Day 168).	Early Term ^{n-2, 5}	Follow Up ³ (21-28 days post last dose)
Sites to provide appropriate snacks and lunch	X	X				X				X	X	
Pedometer eDiary data collection (inc. review)	X	X ¹⁵		X		X		X		X		
MFIS / PGIS (muscle symptoms), PGIS (fatigue symptoms) and PROMIS – Short form FACIT fatigue 13a	X	X		X		X		X		X	X	
SF-36 / BPI and WPAI:SHP		X		X		X		X		X	X	
PGIC (muscle symptoms) and PGIC (fatigue symptoms)										X	X	
12 Minute Walk Test	X ¹⁶	X				X				X	X	
30STS		X				X				X	X	
IMP Capsule Counts			X	X		X		X		X	X	
Eye examination	X ¹⁷					X				X	X	
Wrist radiograph	X ¹⁸											
Concomitant medication review	X-----X											

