4. Only review of concomitant medications, AE's MFIS and 12MWT will be conducted if the subject has discontinued from study drug treatment but has not withdrawn from the study. If the subjects had an ET visit within 2 weeks of either of these a visit is not required.
5. As a minimum, subjects should have review of concomitant medication and AE's, vital signs (including temperature), complete questionnaires, safety laboratory blood (including HbA1c, bone and calcium markers and PK analysis) and urinalysis (including pregnancy tests for WOCBP, drugs of abuse and NTX) and IMP capsule counts.
6. Patient Screen Oversight Committee will review Proforma data and give a decision or request more information within 7 working days.
7. Subjects will be excluded from the study at the Investigators discretion for alcohol and/or drug dependency. Use of opiates/cannabis for medical reasons is acceptable with prescription evidence or at the Investigators discretion.
8. Full physical exam, height and weight at Screening; full physical exam and weight at Baseline; brief, symptom-directed physical exam and weight only at Weeks 12 and 24.

9. Serum FSH testing for post-menopausal females 45 years and older. Serum FSH test must be performed for all women who participate in the REN001-201-DXA sub-study who have not already had an FSH test as part of the parent REN001-201 study.
10. An additional 10 mL blood sample will be taken pre-dose at baseline and the serum will be stored frozen at the central laboratory as a reference sample in the event that re-analysis of protocol stated tests are required.
11. If any clinically significant abnormalities are noted at the Week 24 visit, these should be followed up until resolved.
12. WOCBP will be supplied with urine home pregnancy test kits at Study Center visits to test at Weeks 8, 16 and 20. The Study Center must contact the subject to confirm the pregnancy test result in a timely manner.
13. Blood sample for local genotype testing will only be conducted with prior Sponsor approval and definitive results must be available prior to the Baseline visit.
14. At the Baseline, Week 12 and Week 24 visits, blood samples will be taken pre-dose and then at 1, 2, 3, and 4 hours post-dose. On the other visits, a single sample can be taken at any time post-dose provided the dosing date and time are recorded.
15. Review of Screening (pre-treatment) pedometer data at Baseline.
16. Screening 12MWT must be at least 4 weeks before the Baseline 12MWT.

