Unless stated otherwise, an on-treatment measurement will be any measurement collected (including scheduled and unscheduled visits) up to the date of last dose plus one day for safety endpoints and plus seven days for efficacy endpoints. Drug interruptions will not be considered, i.e., data will not be excluded during a drug interruption if the subject resumes study treatment.

In by-visit summary tables, the baseline will be summarized using all available data, but also for each visit using only the baseline data from subjects with available data at the visit; hence the mean change from baseline will equal the mean observed visit value – mean baseline value.

Throughout this document ‘change from baseline’ refers to the actual change from baseline (i.e., observed visit value – baseline value).

Summary tables will be split by treatment group (REN001 100 mg and placebo). Baseline summary tables (disposition, demography, baseline characteristics, medical history and prior medications) will also include an overall summary.

All data for randomized subjects, who receive at least one dose of study medication, will be listed. For screen failure subjects only disposition (including reason for screen failure), demographics and protocol deviations will be listed.

Data listings will be ordered by treatment group and subject. A subject’s mutational genotype (m.3243A>G, m.8344A>G, mt deletion or Other) will be identified on the listings. Data listings will present study days in addition to dates, where study day is derived as per SDTM guidelines i.e., study day is derived as (assessment date – first day of dosing +1) after the start of dosing and as (assessment date – first day of dosing) before the start of dosing. Hence, the first day of dosing will be identified as Study Day 1.

All statistical analyses will be performed using SAS® (Version 9.4 or higher, SAS Institute Inc., Cary, NC, USA).

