8.3.1. Efficacy Data

As missing data may potentially bias the outcome of the statistical analyses and the subsequent estimation of the magnitude of the treatment effect, different strategies will be applied to provide a balanced assessment of treatment efficacy. This section discusses intercurrent events and missing data in general, but details for each endpoint are discussed in [Section 10](#).

Intercurrent Events

The following potential intercurrent events are currently identified:

- Discontinuation of study treatment
- Specifically, for the 12MWT and 30STS; unwilling or unable to perform the test or walk for the full 12 minutes due to reasons at least possibly related to PMM or study treatment

Subjects who discontinue treatment will be encouraged, where appropriate, to continue in the study with a reduced assessment schedule at Weeks 12 and 24. As a minimum they will be requested to complete the 12MWT and MFIS efficacy assessments at these visits. This allows a treatment policy strategy to be used; for example, the distance walked at the relevant visit will be included in the analysis, regardless of whether the subject has previously discontinued study treatment.

If the subject is unable to perform the 12MWT and/or 30STS at a visit, for reasons at least possibly related to their PMM, their data will be imputed as 0 meters and/or 0 sit to stands for each test, respectively. To assess the subject as unable to perform the 12MWT there must be clear evidence that the subject is not ambulatory at the time of the test.

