Missing PROMIS T-scores as a result of an intercurrent event considered related to a subject's PMM or study treatment will also be imputed using worst case imputation. A blinded Reneo team will adjudicate these cases.

A blinded Reneo team will also adjudicate whether the subject stops their 30STS test prematurely for reasons at least possibly related to their PMM.

Adjudication decisions will be made and documented prior to database locking and the randomization being unblinded.

Missing data

Missing data may arise for the following reasons:

- Withdrawal from the study
- Specifically, for the 12MWT and 30STS; unwilling or unable to perform the test or walk for the full 12 minutes due to reasons unrelated to their PMM or study treatment

The reasons for not performing a test or stopping it prematurely will be collected. Only reasons which clearly indicate that it was unrelated to the subject's PMM or study treatment will be assigned unrelated. The following are examples of why the reason may be regarded as unrelated to the subject's PMM:

- Site is unable to perform the test at the visit
- Subject suffers an accidental injury prior to the visit with clear evidence the subject's PMM and study treatment did not contribute to the injury
- Unexpected fire alarm at the study center means the test has to be aborted

The independent blinded adjudication committee will review all reasons for missing or incomplete 12MWTs and adjudicate whether the reason was related to the subject’s PMM or study treatment. The committee will also adjudicate whether a subject is unable or unwilling to perform a test.

Missing data assessed as unrelated to a subject’s PMM or study treatment will be considered missing at random (MAR). Missing scores (as opposed to intercurrent events) will be handled using either multiple imputation or through mixed effect models for repeated measures (MMRM). Where multiple imputations are used along with imputations for intercurrent events, the multiple imputation step will be performed prior to imputations for intercurrent events. Hence, the MAR imputations will be replaced with those for intercurrent events where applicable.

The table below summarizes the imputation used for the intercurrent and missing data scenarios for the 12MWT:

Type	Case	Handling of Data
Intercurrent Event	Discontinuation of study treatment only; 12MWT still completed	No imputation required. Use 12MWD recorded

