8.4. VISIT WINDOWS

Data will be assigned to ‘analysis’ visits using windowing (see table below). If more than one assessment (including the early termination or unscheduled assessments) falls within the same defined window, the on-treatment assessment closest to the target day with non-missing data will be used for analysis. If the scheduled visit assessment is on-treatment and

within the analysis window, then this will be used irrespective of other unscheduled assessments within the analysis window. If two assessment dates are at the same distance from the target day, the latest on-treatment assessment with non-missing data will be used for analysis. Off-treatment assessments will only be assigned to a visit window in the absence of an on-treatment assessment within the analysis window.

Visit	Target Day	Protocol Visit Window	Analysis Window	Analysis Interval
Baseline	1	NA	$\leq 1^*$	NA
Week 2	14	± 3	8 - 20	13 (± 6)
Week 4	28	± 3	21 – 35 [^]	15 (± 7)
Week 12	84	± 7	63 -105	43 (± 21)
Week 18	126	± 7	106 - 146	41 (± 20)
Week 24	168	± 7	147 - 189	43 (± 21)

* Baseline values must be prior to dosing if time of assessment is recorded.

[^] For pedometer data the lower limit of the analysis window will be widened to allow for the fact that the diary opens 2 weeks prior to the target visit date (Day 14 – 35).

If an unscheduled or early termination visit is mapped to a scheduled visit, then the type of visit will be identified in the appropriate listing together with the visit that it has been mapped to.

Any summaries of screening visit data will always be based on the data collected at the scheduled screening visit. Consequently, if the subject does not have baseline data collected at the baseline visit then the screening data will be used for both the summary of the screening visit and the baseline visit.

Follow-up visits by design are after the last dose of study drug and should not be allocated to on-treatment visits.

Windowing will not be used for the DXA scan data as there is only one measurement post dose.

Data collected outside these windows will not be attributed to an analysis window and will only be listed; unless specified otherwise in [Section 10](#) and [Section 10](#). Any scheduled visit outside the window will be identified on the appropriate listing.

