10.1. PRIMARY ENDPOINT

10.1.1. Primary Estimand

The primary estimand of interest for this study involves a treatment policy strategy. Using this treatment policy strategy, the primary estimand for the primary endpoint is defined as the difference in means between the treatments in the target patient population for the change from baseline at Week 24 in 12MWD, regardless of whether or not the subject continues with treatment or is unable to walk for 12 minutes.

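### SAP 8.4 lets an early-termination walk made within 7 days of the last dose replace a required off-drug Week 24 walk, against the SAP's own treatment-policy rule (minor); separately, the narrowed FAS is missing from SAP Section 14

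*SAP*

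**What the plan says.** **Choice of record.** SAP 8.4 puts scheduled, ET and unscheduled assessments into one analysis window (Week 24: Days 147-189, target Day 168). The scheduled visit has precedence only if it is itself on-treatment. Otherwise an on-treatment assessment is preferred: "Off-treatment assessments will only be assigned to a visit window in the absence of an on-treatment assessment within the analysis window". SAP 8.2 defines on-treatment as "up to the date of last dose plus one day for safety endpoints and plus seven days for efficacy endpoints".

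**Visits after stopping drug.** Protocol 6.8 asks subjects who stop early to "have an Early Termination visit as soon as possible after the subject stops taking study drug"; that visit includes a 12MWT. Protocol 6.9 adds that "they will be strongly encouraged to continue in the study for their Week 12 and Week 24 visits", with the 12MWT in the minimum assessments. Footnote 4 to the schedule (SAP 3.4 and protocol Table 2) gives one exemption: "If the subjects had an ET visit within 2 weeks of either of these a visit is not required".

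**Estimand.** SAP 8.3.1 illustrates the treatment-policy strategy thus: "the distance walked at the relevant visit will be included in the analysis, regardless of whether the subject has previously discontinued study treatment". Protocol 8.5.1 says the same. The first row of the 8.3.1 imputation table, "Discontinuation of study treatment only; 12MWT still completed", uses the recorded distance. SAP 10.1.1 defines the Week 24 estimand "regardless of whether or not the subject continues with treatment or is unable to walk for 12 minutes".

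**Analysis set.** Protocol 8.1.3 defines the FAS as everyone randomised and dosed. SAP 7.4 also removes dosed subjects later discontinued from the study for failing eligibility criteria. The version 2.0 change log records this; Section 14 does not.

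**The concern.** The protocol asks subjects who stop drug to return for an off-drug Week 24 walk, which is what a treatment-policy analysis needs. The 8.4 rule can discard that walk in favour of an earlier one made within a week of the last dose. For those subjects the primary analysis then takes the same Week 24 value as the treatment period restricted analysis (SAP 10.1.5, item 3), which the SAP presents as a different estimand. SAP 10.1.2 refers only to 8.3.1 and gives no window rule of its own, so 8.4 governs.

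On the FAS, someone who reads Section 14 to learn how the analysis departs from the protocol would not see that the primary set has changed. The mFAS and PP sets are subsets of the FAS, so no planned efficacy analysis includes the removed subjects.

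**Working it through.** **The plan's own figure.** Inputs from SAP 3.5: difference 60 m, SD 125 m, two-sided 5%, 90% power. The normal formula gives n = 2 × (1.960 + 1.282)² × 125² / 60² = 91.2, so 92 per arm. The t-based calculation gives 93 per arm (power 90.3%), matching the stated 186. With about 100 per arm, SE = 125 × √(2/100) = 17.7 m.

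**Worked case.** Last dose Day 146, ET walk Day 150, off-drug walk Day 168.
- Day 150 is 4 days after the last dose: on-treatment under 8.2 and inside Days 147-189.
- Day 168 is 22 days after the last dose: off-treatment.
- The visits are 18 days apart, so footnote 4 does not waive the Week 24 visit.
- SAP 8.4 selects Day 150. SAP 8.3.1 calls for the walk at the relevant visit.

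**Required visits only.** For a Week 24 visit on day v, a clash needs an ET walk on or after Day 147, within 7 days of the last dose, and more than 14 days before v. That is ET Days 147 to v − 15. The share assumes even stopping over 168 days and an ET walk within 7 days.

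| Visit day v | ET days | Share of stoppers who stay |
|---|---|---|
| 161 | none | 0% |
| 168 | 147-153 | 7/168 = 4.2% |
| 175 | 147-160 | 14/168 = 8.3% |

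**If subjects also return when footnote 4 does not require it.** The Week 24 walk must itself be off-treatment, so the last dose must be on day v − 8 or earlier (Day 160 for a Day 168 visit). With a later last dose the scheduled walk is on-treatment and 8.4 selects it. The share then depends on the lag from last dose to ET walk.

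| Visit day v | Lag 0 | Lag 7 (maximum) |
|---|---|---|
| 161 | 7/168 = 4.2% | 14/168 = 8.3% |
| 168 | 14/168 = 8.3% | 21/168 = 12.5% |
| 175 | 21/168 = 12.5% | 28/168 = 16.7% |

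**Size.** The number N of subjects who stop drug but stay is not given; 5 to 40 is an assumption, not a bound. Assume also that half are in each arm and that being off drug costs 60 m on mavodelpar only. Expected shift = 0.5 × N × share × 60/100.

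| N | Affected at 4.2% | Shift at 4.2% | Shift at 12.5% |
|---|---|---|---|
| 5 | 0.2 | 0.06 m | 0.2 m |
| 14 | 0.6 | 0.2 m | 0.5 m |
| 20 | 0.8 | 0.25 m | 0.75 m |
| 40 | 1.7 | 0.5 m | 1.5 m |

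The realised shift can have either sign. With N = 20, a 4.2% share and an assumed walk-to-walk SD of 100 m, 200,000 simulated trials gave a mean of 0.25 m (95% range −1.7 to 2.7 m). With no on/off-drug difference the mean was 0 m (about −2.0 to 2.0 m).

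**Week 12.** The same rule affects ET Days 63-69 for a Day 84 visit, but Week 12 is not the primary comparison.

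**FAS.** The number removed is not given. If a restored subject's withdrawal is adjudicated as unrelated, SAP 8.3.1 imputes under MAR within the arm, so the expected shift is about 0 m. Imputation noise over 25 imputations is roughly 125/√25/100 = 0.25 m per subject, or about ±0.5 m at 95%.

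**The case against.** The sentence in 8.3.1 is offered as an example and speaks of the relevant visit; 8.4 can be read as the rule for which record represents that visit. The imputation table asks only for the recorded distance, and the Day 150 walk is recorded, in-window and made after stopping. Footnote 4 already accepts an ET walk in place of a nearby Week 24 visit. SAP 8.4 also requires mapped ET visits to be identified in the listings, so a substitution can be traced.

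Much of this stands. Where footnote 4 waives the visit and none takes place, the ET walk properly stands in. What remains is the required visit: two walks are recorded, one at the scheduled visit, and 8.4 passes over that one because the subject is off drug. This is what 8.3.1 says should not matter.

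On the FAS, the change is stated in 7.4 and in the change log, the SAP promises only that changes will be identified somewhere in the SAP, sponsor and site teams stay blinded, and the set counts and baseline tables will show the exclusions. All of that is right. It leaves the omission from Section 14 and the absence of an efficacy result on all dosed subjects.

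**Conclusion.** The 8.4 rule is wrong as written for the primary analysis, but minor. It affects about 4.2% of stoppers who stay in the study for a Day 168 visit (0% to 8.3% over visits on Days 161-175), with an expected shift at 4.2% of about 0.06 to 0.5 m, at most about 3% of the 17.7 m standard error. The extreme case, 40 such subjects at 12.5%, gives 1.5 m. These figures rest on the assumed N, even stopping, prompt ET walks and a 60 m on/off-drug difference. The reason to act is an unambiguous primary endpoint, not a large bias.

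Stronger readings that a reader might infer are not supported:
- That the SAP abandons treatment policy. It does use off-drug walks whenever no on-treatment walk lies in the window.
- That 12.5% is the typical share for a Day 168 visit. It needs every ET walk exactly 7 days after the last dose, and attendance at visits that footnote 4 does not require.
- That the rule favours mavodelpar. The documents do not settle the direction.
- That the FAS change is concealed or breaches the treatment-policy strategy. It is logged, and it concerns the analysis population rather than the handling of intercurrent events. The gap is mainly one of documentation.

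**What to change.** **SAP 8.4.** For treatment-policy analyses of the 12MWT, use the scheduled Week 12 or Week 24 walk within the window whatever the treatment status; if there is none, use the in-window walk closest to the target day. Keep the on-treatment preference only for the while-on-treatment and treatment period restricted analyses (10.1.5, items 2 and 3).

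**SAP 7.4 and Section 14.** List the FAS change in Section 14. Add one sensitivity analysis of the primary endpoint on all randomised and dosed subjects, handling withdrawals by the 8.3.1 table.

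**Cost.** One or two sentences and a derivation flag for 8.4; one line and one extra table for the FAS. No new data, and no change to sample size or trial conduct. The added sensitivity analysis may include a few ineligible subjects, which is a reason to present it beside the primary result rather than in its place.
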